8. INTERVENTION DISCONTINUATION

Patients and their parents have the right to withdraw consent/assent or discontinue participation at any time without penalty or any impact on the child's care. Because this is an exploratory clinical

trial, we will not discontinue participation based on missed attendance to treatment sessions. There will be no temporary discontinuations from treatment or study participation. The PI may withdraw a patient/parent dyad from the study for one or more of the following reasons:

- Failure to follow instructions of the PI or study staff.
- The PI decides that continued participation would be harmful (e.g., patient reports increased emotional or physical distress from exposure therapy)

Patients and parents will be asked permission to use data collected from the study if they are asked to discontinue or decide to withdraw from the study.

9. STATISTICAL CONSIDERATIONS

9.1 General Design Issues

To characterize feasibility of a future hybrid effectiveness-dissemination trial of PRVR in routine physiotherapy practice. Hypotheses: PRVR participants will have (1) high patient-reported treatment satisfaction and high clinician-rated patient engagement scores; Clinicians will report high clinical proficiency and self-efficacy in using PRVR.

Analysis Plan: *Satisfaction.* We will examine mean satisfaction scores, clinician rated engagement scores, and clinician proficiency and efficacy with PRVR clinical use.

Adherence/retention. We will examine mean adolescent adherence to survey completion, percent of patients who dropout prior to treatment completion, and VR side effects reported.

Health care costs and pain medication use. We will examine health care and pain medication use by calculating totals via healthcare cost surveys and compared across timepoints.

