This is a single arm feasibility study. A “**participant**” in this study is defined as a child and at least one parent. The **primary outcomes** are feasibility, acceptability, and utility of VR. The **secondary outcomes** are physical function (child only) and pain-related fear and avoidance (child).

Interventions and Duration

All participants will receive an Oculus Quest 2 virtual reality (VR) headset for use during their treatment at the PPMC. VR will supplement treatment and be used in session (either in-person or telehealth) and at home as part of their prescribed treatment homework.

Sample Size and Population

Patients who meet eligibility criteria will be referred to the study by their clinician at clinic appointments.

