2. BACKGROUND AND RATIONALE

2.1 Background and Significance

Overall Scientific Premise. Chronic musculoskeletal (MSK) pain in adolescence is a significant public health concern with median prevalence rates of 11 to 38%¹⁻², with 3 to 5% of adolescents suffering from significant pain-related disability²⁵⁻²⁶, costing society \$19.5 billion annually in the US alone³. Notwithstanding the personal suffering and persistent physical and economic consequences for families, chronic pain in adolescence can predispose the development of adult chronic pain²⁷. Progressively increasing activity in the presence of pain is critical for effective functional restoration in chronic MSK pain in adolescents⁶ and adults⁷⁻¹³ with physiotherapy (PT) a critical ingredient¹⁴. Despite the widespread use of Standard Physiotherapy Rehabilitation (SPR)¹⁵, daring to increase movement while in pain can often feel physically and emotionally unattainable with fear of pain a particularly salient influence on pain outcomes¹⁶⁻¹⁹,

hindering clinical improvement²⁰. Virtual reality (VR) has the potential to break the vicious cycle of fear of movement and avoidance during PT. VR provides access to a multisensory, three-dimensional (3D) immersive experience to overcome obstacles that seem insurmountable in the real world. Thus, the current study tests pain rehabilitation virtual reality (PRVR) for adolescents with chronic MSK pain. PRVR was created with input from a multidisciplinary collaborative team of pediatric rehabilitation providers and patient end users, alongside VR technology developers in response to the growing need for VR programming specific to pediatric chronic pain populations whose mobility has been limited due to pain, fear and activity avoidance. PRVR gamifies PT, helping patients increase their range of motion and become more comfortable moving their bodies to achieve game objectives. The games offer a combination of acute distraction from pain, reinforcement of movement, and progressive increases in range of motion. With evidence that VR holds promise for chronic pain rehabilitation in adults^{23,24,28} and compelling preliminary results from our feasibility-tested immersive PRVR intervention, this feasibility study will provide the necessary findings to support or refute the feasibility of scale implementation of PRVR, a tailored treatment option for adolescents struggling with persistent MSK pain, fear, and disability.

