of outpatient PT with each patient serving as their own control (NCT03874507). Patients moved significantly more when participating in PRVR compared to SPR (1120.88 meters vs 672.65 meters $p = 5.47E-08$; **Figure 5**). When stratified by therapy target (upper vs lower) PRVR treatment was also associated with more movement of the appropriate limbs, lower ($p < 0.001$) and upper ($p = 0.01$). Pediatric users reported significantly less pain when using VR (88%) compared to adults (50%) and virtually all patients reported enjoying the VR experience (96% adult users; 100% pediatric users). (Caruso et al., *in preparation*). These results suggest marked increases in movement, potential pain relief, and a fun experience using VR in PT and warrants examination for cumulative effects over multiple treatment sessions.

Feasibility and Acceptability Data. PRVR feasibility testing (**Mayday Fund supported**) included 17 participants (13 female, 4 male), mean age 13.24 (range 7-17), completing a total of 63 sessions. Overall reports of immersion were high ($M = 28.98$, $SD = 4.02$ out of 40). Analysis of 45 sessions from 13 patients entered into the NVivo qualitative data analysis program revealed: 1) positive experience (i.e., enjoyed it, would like to utilize the VR program again, felt it was a helpful tool), 2) feeling distracted from pain while engaged in VR, 3) increased physical function/mobility, and 4) reduced pain behaviors/symptoms during VR (Griffin et al., *in submission*). These results suggest that Fruity Feet has the right mix of immersion, fun and PT movement capabilities to provide targeted and effective pain physiotherapy in VR.

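### Section 9.1 leaves the treatment-adherence data collected weekly out of the feasibility analysis, rests four hypotheses of high scores on means with no interval or criterion, and ties utility to no measure in the available text

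*Combined protocol and SAP*

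**What the plan says.** The Précis (Design and Outcomes) says that the primary outcomes "are feasibility, acceptability, and utility of VR". The aim in Section 9.1 is "To characterize feasibility of a future hybrid effectiveness-dissemination trial of PRVR in routine physiotherapy practice". Two sentences of hypotheses follow. One concerns patients: "PRVR participants will have (1) high patient-reported treatment satisfaction and high clinician-rated patient engagement scores". The other concerns clinicians: "Clinicians will report high clinical proficiency and self-efficacy in using PRVR". That makes four scores expected to be high.

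For those scores the analysis plan reads "We will examine mean satisfaction scores, clinician rated engagement scores, and clinician proficiency and efficacy with PRVR clinical use". For adherence and retention it reads "We will examine mean adolescent adherence to survey completion, percent of patients who dropout prior to treatment completion, and VR side effects reported". Section 9.1 does not mention utility, attendance at sessions, home use of VR or any interval.

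Four other places bear on this:
- Section 7.6 (Adherence Data) has the coordinator collect data on adherence to the treatment protocol every week, for quarterly review by the investigator and the monitoring committee.
- Sections 3 and 5.1 make VR part of both the treatment sessions and the prescribed homework.
- Section 8 says missed sessions will not lead to discontinuation.
- Section 5.4, headed Adherence Assessment, describes monitoring and payment but defines no adherence measure.

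**The concern.** Whether adolescents attend sessions and use the headset at home as prescribed is central to the feasibility of a clinic-plus-home VR treatment. The data are to be collected, but the only adherence that Section 9.1 analyses is adherence to questionnaires. The remaining retention measure, dropout, does not fill the gap, because a child who misses sessions stays in the study. A favourable dropout figure could sit alongside poor exposure to the intervention.

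The second part concerns how the scores will be read. Section 2.1 says the findings will "support or refute the feasibility of scale implementation of PRVR". A mean with no interval, set against the word high with no value attached, leaves that reading open until after the data are seen. The third part is that one of three primary outcomes, utility, is not connected to a measure in the statistical section. The results are meant to inform a later hybrid effectiveness-dissemination trial, so an over-favourable picture would carry forward.

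**Working it through.** The plan states no figure that can be reproduced. The visible text gives no sample size (the Précis heading for it holds only the referral sentence), no standard deviation, no cut-off and no expected dropout. The check is therefore a comparison of sections, followed by arithmetic on assumed sizes.

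**1. What dropout captures.** Let N children enrol, D drop out, and M stay enrolled but miss much of the sessions or home VR.
- Planned figure: D/N.
- Share not receiving the intervention as prescribed: (D + M)/N.
- Difference: M/N.

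Section 8 allows M to be above zero, and the documents do not let M be estimated. Each such child adds 1/N: 5.9 percentage points at N = 17 (the size of the earlier PRVR test in Section 2.2), 5.0 at 20, 3.3 at 30 and 2.5 at 40. The weekly data in Section 7.6 may be able to show M, depending on what they record.

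A related gap is the reference point for dropout. Sections 3 and 5.1 both accept the clinician's judgement as an end of treatment and are compatible with each other. Neither they nor Section 8 say how the analysis counts a child who stops attending without clinician discharge.

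**2. Precision of the dropout percentage.** Exact (Clopper-Pearson) 95% intervals, for assumed counts near 20%:

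| Dropouts / N | 95% CI |
|---|---|
| 3/17 | 3.8% to 43.4% |
| 4/20 | 5.7% to 43.7% |
| 6/30 | 7.7% to 38.6% |
| 8/40 | 9.1% to 35.6% |

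**3. Precision of a mean.** The 95% half-width in SD units is t(0.975, n-1)/√n.
- Children: 2.120/√17 = 0.51; 2.093/√20 = 0.47; 2.045/√30 = 0.37; 2.023/√40 = 0.32.
- Clinicians, who are the unit for proficiency and self-efficacy: 3.182/√4 = 1.59; 2.571/√6 = 1.05; 2.365/√8 = 0.84.

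**4. Clustering in clinician-rated engagement.** Children rated by the same clinician may have correlated scores. Assume 30 children, 6 clinicians with 5 children each, and an intraclass correlation of 0.1 to 0.3. The variance inflation is 1 + (5-1) × ICC, and t has 6-1 = 5 degrees of freedom.
- ICC 0.1: inflation 1.4; 2.571 × √(1.4/30) = 0.56 SD.
- ICC 0.3: inflation 2.2; 2.571 × √(2.2/30) = 0.70 SD.

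The interval that treats the 30 children as independent is 0.37 SD, so ignoring the clinician would make it clearly too narrow.

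**5. Utility.** Section 9.1 does not mention it, and no other available section ties it to an instrument, respondent or time point. The clinician survey in Section 6.2 is described as documenting VR use for safety. Instruments are deferred to Supplemental Materials III.

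**The case against.** The strongest reply is that this is a single-arm, exploratory study whose aim is to characterise feasibility, so description is the right analysis and no test or pass mark is owed. That stands. A reader might infer that the plan must set boundaries for progressing, modifying or not progressing. The documents do not support this: nothing in them makes the later trial depend on a score, and the phrase about supporting or refuting feasibility is in the background section. If means and intervals are published, readers can also apply their own cut-off.

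A reader might infer that utility is not measured, or that no target exists. That also goes too far. Supplemental Materials III and the grant proposal were not available, and Sections 1 and 4 are absent from the visible text; any of these may hold a measure or a target. What can be said is that Section 9.1 neither states nor cites one.

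A reader might take the earlier PRVR test, where Section 2.2 says "Overall reports of immersion were high" without a cut-off, as proof of how these results will be judged. Immersion is not one of the four hypothesised scores, so it measures nothing here.

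On adherence, the data are not ignored, since the monitoring committee reviews them quarterly. The investigator may also withdraw a family for failing to follow instructions, so some non-adherent children could become dropouts. But that is discretionary, and oversight review is not a reported feasibility result. It is also fair that adherence to the treatment protocol is undefined: it could mean attendance, home use or therapist fidelity. The fix must therefore say which.

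**Conclusion.** The point holds, and should be acted on, at moderate weight. Its firmest part is adherence: followed as written, Section 9.1 can overstate feasibility, because children who miss sessions or home VR need not appear in any planned summary. The direction is clear. The size is not, because the number of such children and N are both unknown; each one is worth 2.5 to 5.9 percentage points at an assumed 40 to 17 children.

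The absence of intervals matters because the likely precision is low: about 0.3 to 0.5 SD for a mean over 17 to 40 children, 0.8 to 1.6 SD over 8 to 4 clinicians, and an interval of roughly 26 to 40 percentage points in width for dropout near 20%. All of these rest on assumed sizes. The clustering figures rest further on an assumed ICC and equal numbers of children per clinician.

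The undefined use of high and the unlinked utility outcome are missing specification, not errors, and could be resolved by documents not available here. Confidence is medium for that reason.

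**What to change.** Amend Section 9.1 before outcome data are examined:

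(a) Add the weekly treatment-adherence data to the feasibility analysis and state which component is summarised, for example session attendance or prescribed home VR use. Use all enrolled children as the denominator for adherence and for dropout. For analysis only, state how a child who stops attending without clinician discharge is counted.

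(b) Report each mean with a 95% CI and each percentage with an exact 95% CI, giving the numbers of children and clinicians. If a score is rated more than once per child, average within child first. Allow for clustering by clinician in clinician-rated scores.

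(c) Either give the sponsor's numeric value for a high score in advance, citing it if it already exists elsewhere, or reword all four hypotheses as descriptive.

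(d) Name the utility measure, or cite where it is given.

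Progression boundaries are optional.

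The cost is SAP wording and simple interval calculations, with no new visits. Item (a) is cheap provided the weekly records hold the chosen component, which the text does not confirm. The downside is a little more analysis work and possibly a less favourable feasibility picture.

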10. DATA COLLECTION AND QUALITY ASSURANCE

10.1 Data Collection Forms

The majority of the research data, including self-reported questionnaires, informed consent forms, appointment tracking, case report forms, adverse events, serious adverse events, protocol deviations, and unanticipated problems will be sourced and captured electronically by participant via REDCap. If participants opt to complete daily diaries, daily check-in surveys will be collected electronically by participant via LifeData. Data collection will occur either in-person on an encrypted study iPad, or at home via electronic surveys.

REDCap's features include research data collection instruments (surveys and forms), and an e-Consent Auto-Archiver Framework. The e-Consent Framework platform will be used to consent patients on site using a computer-based consent form rather than traditional paper documentation.

LifeData is a mobile application to collect experience sampling, ecological momentary assessment, and electronic check-ins. This app will be used to easily push notifications to child and parent devices to collect Daily Check-in data.

Word document versions of the REDCap data collection instruments can be found in the MOP Supplemental Materials Section:

- Supplemental Materials I: Electronic Case Report Form (eCRF) Templates
- Supplemental Materials II: Research Consent and Assent Forms
- Supplemental Materials III: Self-Reported Questionnaires

The CRC will be responsible for maintenance of all data collection forms, and will include any updates in the monthly report to the NIAMS via NCR.

10.2 Data Management

All questionnaire data collected for the study will be exported into SPSS, SAS or R via REDCap. Treatment session audio/video recordings may be recorded digitally and saved on the secure, private drive on the server and only personnel associated with the study will have access to the files.

10.3 Quality Assurance

10.3.1 Training

Stanford University uses the “CITI” training program (Collaborative Institutional Training Initiative; <https://www.citiprogram.org/>). All staff must pass required tests on each module. A refresher course must be passed every 3 years.

Per NIH requirements, all staff will be trained in Good Clinical Practice (GCP), consistent with principles of the International Conference on Harmonisation (ICH) E6 (R2). The CRC will be responsible for maintaining documentation of all CITI and GCP training certifications.

An outpatient team of licensed Physical Therapists at each clinical site will provide study intervention sessions, trained in this modality of treatment by [name] with ongoing consultation from [name] PT, DPT (expert in physical rehabilitation for chronic pain) and [name] (expert in virtual reality intervention administration).

The PI will be responsible for and oversee all training of research personnel in GCP and the delivery of study interventions. All members of the research team will be trained on the contents of this document (MOP) and relevant study materials prior to beginning work on the study.

The PI and CRC will hold primary responsibility for study data quality control. To address quality control methods, all data will be entered into REDCap using standardized electronic case report forms (eCRFs).

10.3.2 Quality Control Committee

The PI and research coordinator will be hold primary responsibility for study data quality control. To address quality control methods, chart data will utilize standardized collection forms. For data entry of study information, a portion of files will be re-entered by a separate person, to check for consistency. If consistency is low, the entire data set will be re-entered.

10.3.3 Metrics

All self-report outcome measures have demonstrated psychometric soundness, including reliability and validity.

10.3.4 Protocol Deviations

Each protocol deviation (PD) will be captured and documented, by participant, in the Protocol Deviation Tracking Log eCRF (MOP Appendix E). All PDs will be collated and reviewed by the CRC and study PI.

A major protocol deviation or violation includes any procedure that differs from the IRB-approved protocol that was intended to eliminate an immediate hazard to the participant, was harmful, or is possible serious or continue non-compliance by a study staff member.

Major protocol deviations will be communicated to the PI immediately. All events will be communicated to the NIAMS via NCR within 48 hours of the PI becoming aware of the event.

Protocol deviations/violations that occur but do not affect participant safety will be submitted as part of the quarterly reports distributed to the SMC and subsequently shared with the NIAMS.

10.3.5 Monitoring

The study will be monitored by the research coordinator regularly throughout the collection of data. Oversight of this clinical trial is provided by the Principal Investigator (PI), [name] and a Study Monitoring Committee (see section 7.6).

11. PARTICIPANT RIGHTS AND CONFIDENTIALITY

11.1 Institutional Review Board (IRB) Review

This protocol and the informed consent document (MOOP Supplemental Materials II) and any subsequent modifications will be reviewed and approved by the Stanford IRB responsible for oversight of the study.

11.2 Informed Consent Forms

A signed consent form will be obtained from each parent participant, and a signed assent form for each child participant. For participants who cannot consent for themselves, such as those with a legal guardian (e.g., person with power of attorney), this individual must sign the consent form. The consent form will describe the purpose of the study, the procedures to be followed, and the risks and benefits of participation. A copy will be given to each participant or legal guardian and this fact will be documented in the participant's record. Per IRB requirements, any participant who turns 18 years of age while actively enrolled during the course of study will be contacted and consented as an adult.

11.3 Participant Confidentiality

Any data, specimens, forms, reports, video recordings, and other records that leave the site will be identified only by a participant identification number (PID) to maintain confidentiality. All records will be kept in a locked file cabinet. All computer entry and networking programs will be done using PIDs only. Information will not be released without written permission of the participant, except as necessary for monitoring by IRB, the FDA, the NIAMS, and the OHRP.

11.4 Study Discontinuation

The study may be discontinued at any time by the IRB, the NIAMS, the OHRP, the FDA, or other government agencies as part of their duties to ensure that research participants are protected.

12. COMMITTEES

Steering committee – Study PI, Co-Investigators, and Research Coordinator for this study will meet monthly to discuss study progress relative to milestones, coordinate efforts, and review any protocol deviations or other issues requiring adjustment.

Safety Monitoring Committee – The Study PI and Study Monitoring Committee (Section 7.6) will meet quarterly to review study accrual, status of enrollment, adherence to data regarding study visit and intervention, and adverse events.

13. PUBLICATION OF RESEARCH FINDINGS

As an NIH-funded Clinical Trial this study will be registered at, and will submit summary results information to, ClinicalTrials.gov for public posting. Publication of the results of this trial will be governed by the policies and procedures developed by the Steering Committee.

